1. INTRODUCTION

1.1 Background

During the past several years, *C. difficile* Infection (CDI) has become more frequent and severe, more refractory to standard therapy, with predictable recurrence rates of 25% after standard therapy^{1,2}. It is now accepted that the disruption of the normal balance of colonic microbiota secondary to antibiotics facilitates the development of CDI and improvements in the diversity and quantity of microbiota is associated with recovery of infection and prevention of disease recurrence. Studies have shown that subjects with recurrent CDI (RCDI) have decreased diversity of colonic flora with absolute reductions in counts of anaerobic species of *Bacteroidetes* and *Firmicutes* in their stool compared to subjects recovering from single episodes of CDI³. Numerous case reports and retrospective case series have demonstrated the benefit of intestinal microbiota transplantation (FMT) in subjects with severe or RCDI with cure rates over 80%-90%⁴⁻⁸, making FMT standard therapy when multiple recurrences are seen⁹. FMT involves administration of a suspension of intestinal bacteria obtained from a healthy individual into the GI tract of a patient with RCDI to promote normalization of flora⁶.

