4.2 Exclusion Criteria

- 4.2.1 Unable to take capsules orally.
- 4.2.2 Requiring systemic non-*C. difficile* antibiotic therapy within 14 days prior to FMT.
- 4.2.3 Unwilling to stop taking non-dietary probiotics 24-96 hours prior to FMT.
- 4.2.4 Unable to stop taking bile acid sequestrants (e.g. cholestyramine) 24-96 hours prior to FMT.
- 4.2.5 Unable to stop use of drugs with CDI activity: oral vancomycin, oral or IV metronidazole, fidaxomicin, rifaximin or nitazoxanide 24-96 hours prior to FMT and after FMT.

4.2.6 Receipt of CDI monoclonal antibodies as treatment for the most recent bout of CDI.

4.2.7 Life expectancy of < 6 months.

4.2.8 In the opinion of investigator, subject for any reason should be excluded from the study.

4.3 Vulnerable Population in Research:

The elderly population particularly is susceptible to recurrent *C. difficile* infection (CDI) and some elderly patients may be cognitively impaired. Informed consent can be obtained from legally authorized representatives (LAR) if potential subjects have condition or circumstances that could impact their ability to make decision or consent. These subjects may include but are not limited to the cognitively impaired, demented, incapacitated, or otherwise mentally or physically incapable of communication. Before their enrollment, the study coordinators must be certain that a caretaker can properly record data called for in the study.

The investigators or designee will assess subjects on their abilities to understand information and express a reasoned choice concerning the nature of the research, consequences of participations for the subject's own situation, and consequences of the alternatives to participation. The investigators or designee will ask questions about the main elements of the study and judge whether the potential participant has a clear understanding.

When an LAR agrees to the participation of the subject in the study, the consent would be obtained either from the patient's legal guardian with the authority to make decisions regarding medical treatment (with proper paperwork to establish this) or a person designated as a surrogate decision-maker by the patient in a medical power of attorney or Advance Directive. The investigator or designee will ask for a copy of the legal document from the authorized representative. The LAR and the person obtaining consent would personally sign and date the consent form. A copy of the signed consent document will be given to the LAR.

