4.7 Lost to Follow-up

If subjects miss a treatment or follow-up, three attempts will be made by telephone or e-mail to contact and locate subjects. The contact attempts will be recorded on the study exit form.

4.8 Receipt of Systemic Antibiotics, Non-Dietary Probiotics and Bile-acid Sequestrants during the Trial

If a subject takes a systemic (non-topical) antibiotic within 60 days after FMT treatment, they will be excluded from the efficacy part of the study and only followed for safety. Exclusion from efficacy means subjects will no longer provide stool specimens. However, subjects will continue to have phone visits and submit diaries till 180-200 days (the end of the study) for safety assessment (AEs). If they take systemic antibiotics more than 60 days after FMT treatment, they will be included in all aspects of the study.

Subjects will be recommended not to use non-dietary probiotics and bile-acid sequestrants within 60 days after FMT treatment; however, subjects who take probiotics and bile-acid sequestrants within 60 days after treatment will not be excluded and continue to be followed for efficacy and safety.

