6. TREATMENT FAILURES AND RETREATMENT

Treatment failure is defined as the presence of diarrhea (passage of ≥ 3 watery stools per 24-hour period for two consecutive days) and *C. difficile* toxin A/B positive stool within 60 days of FMT treatment and receipt of anti-*C. difficile* antibiotics.

If diarrhea (passage of ≥ 3 watery stools per 24-hour period for two consecutive days) occurs and CDI recurrence is suspected, subjects should inform study team and be recommended to contact their physician to perform a stool test for *C. difficile*. EPDL will test scheduled stool specimens and any unscheduled illness stool submitted up to days 60-70 after treatment for *C. difficile* toxins A/B in weekly batches but this should not delay treatment. If the test is positive, they should be treated by their physician. The Principal Investigator will be available for consultation with the attending physician. Subjects who are determined treatment failures by the investigator will not be followed further for clinical parameters. They will be offered FMT retreatment with maximum dose (200g) from a different donor product if the subject and their physician wish to pursue this treatment. After at least 10-20 days of anti-CDI antibiotics (vancomycin or fidaxomicin) subjects will be eligible for second FMT after 24-96 hour washout. If there is a delay between completing treatment and second FMT, the subject will receive at least four days of vancomycin or fidaxomicin prior to FMT (PI can call in prescription if needed) to complete the treatment 24-96 hours before second FMT. Subjects will be recommended to follow a clear liquid diet the entire day before retreatment clinic visit. Bowel preparation and Imodium will not be required before retreatment. During retreatment clinic visit, vital signs and weight will not be assessed and subjects will be observed for 30 minutes after dosing.

Retreatment Dosage: Day 1 (Clinic Visit)

- Subjects are recommended to continue clear liquid diet until 1 hour after retreatment.

- Perform urine pregnancy test on all female subjects of childbearing potential prior to FMT administration.
- Administer Day 1 dose and dispense Day 2 dose.
- Observe the subject for 30 minutes after dosing.
- Remind subject that Day 2 dose should be taken the next morning on empty stomach with water and release the subject.

Retreatment Dosage: Day 2 (Phone Visit)

- Ask that subject has taken the Day 2 dose.
- Ask for any adverse events since Day 1 assessment.

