- Confirm that the C. difficile antibiotic was stopped 24-96 hours before the visit.
- Perform urine pregnancy test on all female subjects of childbearing potential prior to FMT administration.
- Weight and vital signs (blood pressure, heart rate, respiration rate, oral temperature) will be collected pre-treatment.
- Administer Day 1 dose and dispense Day 2 dose.
- Ask subject if experienced any objectionable taste or smell or difficulty swallowing the capsules and general reaction on taking PRIM-DJ2727 capsules.
- Observe the subject for 1 hour after dosing for any adverse events.
- Collect post-treatment vital signs (blood pressure, heart rate, respiration rate, oral temperature).
- Remind subject that Day 2 dose should be taken the next morning on empty stomach with water.
- Remind subject to continue taking routine prescription medications as needed, but antibiotics, non-dietary probiotics and bile-acid sequestrants may not be taken.
- Release subject with IRB approved aftercare instructions, follow-up paper diaries, visit scheduler, safe antibiotics list and specimen request form.

Second Treatment Dosage: Day 2 (Phone Visit)

- Ask that subject has taken the Day 2 dose.
- Ask for any adverse events since Day 1 assessment.
- Remind subject to follow the aftercare instructions provided on Day 1.
- Remind subject to continue taking routine prescription medications as needed, but antibiotics, probiotics and bile-acid sequestrants may not be taken.
- Remind subject to completely fill the diaries, and submit diaries and stools at follow-up visits according to schedule and instructions provided by study personnel.
- A form letter to subject's physician about FMT completion may be faxed or emailed.

Follow Up and Safety Assessment Period (Phone Visits): Post Treatment Days 1(+3), 7(+3), 14(+3), 30(+10), 60(+10), 90(+10) and 180(+20).

- Assess subject for any adverse events, new illness symptoms, worsening of baseline illnesses including adverse events of special interest (new or worsening autoimmune conditions and metabolic syndrome) and change in medication. Review and assess subject-reported weight data from diaries for AE (>5% change from baseline weight) at days 60 and 180 phone visits.

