7.3 Clinical Response Evaluation

The clinical evaluation will include an evaluation of CDI recurrence to assess clinical response on each follow-up contact for 60 days after FMT.

If subjects experience diarrhea (3 or more watery stools/day for two consecutive days) and suspect CDI recurrence, they should inform the study team and be recommended to contact their physician to perform a stool test for *C. difficile*. EPDL will test scheduled stool specimens and any unscheduled illness stool submitted up to days 60-70 after treatment for *C. difficile* toxins A/B in weekly batches but this should not delay treatment. If the test is positive, they should be treated by their physician. The Principal Investigator will be available for consultation with the attending physician. A form letter may be faxed or emailed to subject's physician about CDI recurrence.

Subjects requiring a systemic Non- *C. difficile* antibiotic within 60 days following FMT treatment will be excluded from the study for efficacy analysis, but will be followed for safety. Exclusion from efficacy means subjects will no longer provide stool specimens. However, subjects will continue to have phone visits and submit diaries till 180-200 days (the end of the study) for safety assessment (AEs). Subjects requiring a systemic Non- *C. difficile* antibiotic 60 days after FMT treatment will continue to be followed for efficacy and safety.

Subjects will be recommended not to use non-dietary probiotics and bile-acid sequestrants within 60 days after FMT treatment; however, subjects who take probiotics and bile-acid sequestrants within 60 days after treatment will not be excluded and continue

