10.2.3 Analysis Populations

Two primary analyses will be performed:

- 1) Analysis for safety and efficacy between three groups (1-3) receiving varied doses of lyophilized product generated from stool (50g for both treatment days; 100g on the first treatment day and 50g on the second treatment; 100g for both treatment days)
- 2) Analysis for safety and efficacy between two groups (3 and 4) with and without bowel preparation and Imodium receiving same high doses of lyophilized product (100g for both treatment days).

- All analyses will be conducted using the intent-to-treat population. Intent-to-treat is defined as all subjects who have started the procedure.
- Listings and summary tables with descriptive statistics will be prepared for demographic data (gender, date of birth, race/ethnicity), and medical history data.

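### The plan analyses efficacy in everyone who started treatment, yet excludes dosed subjects who take an antibiotic within the 60-day primary window, and does not say which rule governs

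*Combined protocol and SAP*

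**What the plan says.** Section 10.2.3 (Analysis Populations) reads: "All analyses will be conducted using the intent-to-treat population. Intent-to-treat is defined as all subjects who have started the procedure". It names no exception and no per-protocol or evaluable set, and it applies to both primary comparisons (groups 1 to 3; group 3 against group 4).

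Under section 4.8, if a subject "takes a systemic (non-topical) antibiotic within 60 days after FMT treatment, they will be excluded from the efficacy part of the study", follow-up continues for safety only. Section 7.3 (Clinical Response Evaluation) says that subjects needing a systemic non-C. difficile antibiotic in the same period "will be excluded from the study for efficacy analysis, but will be followed for safety". Both sections then explain: "Exclusion from efficacy means subjects will no longer provide stool specimens". Phone visits and diaries go on to the end of the study, for adverse-event assessment.

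The primary efficacy endpoint is prevention of CDI in the 60 days after FMT (sections 2 and 9.11). Section 6 defines failure as diarrhea with a "toxin A/B positive stool within 60 days of FMT treatment and receipt of" anti-C. difficile antibiotics.

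Section 10.2.4 mentions a target of 360 evaluable subjects without defining evaluable.

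**The concern.** The exclusion period and the primary endpoint window are the same 60 days. A subject dosed on day 1 and given an antibiotic on day 20 counts in the primary efficacy analysis under 10.2.3 and does not count under 4.8 and 7.3. Whoever runs the analysis must choose, and as written the choice could be made after outcomes are known.

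The exclusion is not neutral in principle. Antibiotic use happens after randomisation, and section 1.1 states that "disruption of the normal balance of colonic microbiota secondary to antibiotics facilitates the development of CDI". Removing users therefore selects subjects on an event that the protocol ties to the outcome. Group 4 is unblinded, so equal antibiotic use in groups 3 and 4 is not assured.

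Stopping stool collection also has a lasting consequence. Failure requires a positive toxin test, and section 9.12 has the study laboratory test stools collected up to day 60. For excluded subjects that testing ends. If intent-to-treat is later held to govern, those samples cannot be recovered.

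**Working it through.** **Do the sections reconcile?**

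- *Population.* 10.2.3 includes all who started. 4.8 and 7.3 remove antibiotic users. No text in 10.2 makes one subordinate to the other.
- *Is it only a stool-collection rule?* Both sections give that gloss, but 7.3 also names the efficacy analysis. In addition, 4.8 contrasts these subjects with users of probiotics and bile-acid sequestrants, who stay in follow-up for efficacy.
- *Is the outcome still captured?* Section 7.2 phone visits ask about diarrhea up to day 60 and cover "and metabolic syndrome) and change in medication"; suspected recurrence is referred to the physician for testing. For excluded subjects, however, 4.8 and 7.3 say that contact continues for adverse events. Section 9.1.1 does not record CDI recurrence as an adverse event unless hospitalization of at least 24 hours is required. Capture is possible but not assured.

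**How far could the choice move the result?** The plan gives no figure for this. It states neither the share taking an antibiotic nor their recurrence risk, so what follows is an illustration.

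Inputs from section 10.2.2: planned efficacy 70/80/88% in groups 1/2/3, that is failure f = 0.30/0.20/0.12, with 90 per group. Assumptions:

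- a = share taking a non-C. difficile antibiotic by day 60, equal in all arms;
- r = recurrence risk in users relative to non-users;
- k = share of users' failures removed by the exclusion (the rest occur before the antibiotic and are kept).

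Formulas:

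- non-user failure q = f / (a·r + 1 − a)
- apparent failure = [(1 − a)q + (1 − k)·a·r·q] / [1 − a(1 − r·q) − k·a·r·q]
- analysed n per group = 90 × the denominator

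With a = 0 the formula returns the planned 70/80/88% and the 18.0-point difference.

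Group 1, a = 0.10, r = 1, k = 0.5: q = 0.30; numerator 0.270 + 0.015 = 0.285; denominator 1 − 0.070 − 0.015 = 0.915; failure 0.3115, efficacy 68.9%.

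Group 1, a = 0.10, r = 3, k = 1: q = 0.30/1.2 = 0.25. All users are removed, so failure is 0.25 and efficacy 75.0%.

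| Case (a = 0.10) | Groups 1/2/3 (%) | Group 3 − group 1 (points) |
|---|---|---|
| Planned, no exclusion | 70 / 80 / 88 | 18.0 |
| r = 1, k = 0.5 | 68.9 / 79.1 / 87.4 | 18.6 |
| r = 1, k = 1 | 70.0 / 80.0 / 88.0 | 18.0 |
| r = 1.5, k = 0.5 | 69.8 / 79.7 / 87.7 | 18.0 |
| r = 2, k = 0.5 | 70.6 / 80.2 / 88.0 | 17.4 |
| r = 3, k = 1 | 75.0 / 83.3 / 90.0 | 15.0 |

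In the r = 2, k = 0.5 case, changing uptake to 5% or 20% gives a difference of 17.7 or 17.2 points. The analysed n at 10% uptake is about 81 to 84 per group instead of 90.

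The apparent rate depends only on f, a, r and k. If two arms share the same f and the same a, r and k, they show the same apparent rate, so no difference appears where none exists. Differential uptake between arms is not modelled.

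**The case against.** The strongest reply is that the exclusion is defined operationally. Both 4.8 and 7.3 say it means no further stool specimens, and 10.2.4 speaks of evaluable subjects, so an evaluable efficacy set may have been intended. That may be what the authors meant, but it does not settle the matter. 7.3 also says efficacy analysis, evaluable is not defined, and 10.2.3 allows no exception.

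A second reply is that a declared modified population, with full intent-to-treat as sensitivity, would also remove the contradiction. That is true. Keeping users is preferable because 10.2.3 already commits to it and because uncollected samples cannot be restored.

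A third is that section 10.2.6 expects only trends and that the illustrated shift is modest in the middle case. Both are true, but a trend still needs a defined denominator.

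A reader might infer three stronger things that the documents do not support:

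- *That the exclusion inflates efficacy.* With no excess risk and half of users' failures kept, apparent efficacy falls and the arm difference widens. The direction is indeterminate.
- *That 4.8, by covering any systemic antibiotic, deletes the failures themselves, since failure requires an anti-C. difficile antibiotic.* Section 6 classifies those subjects as failures with their own retreatment path, 7.3 limits the exclusion to other antibiotics, and 4.2.2 and 4.2.5 ("Unable to stop use of drugs with CDI activity") treat the two classes separately. This is a difference in scope to align, nothing more.
- *That recurrence in excluded subjects is lost altogether, or conversely that it remains largely captured.* Physician testing and phone contact remain, but nothing assures that the efficacy outcome is recorded.

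**Conclusion.** The point holds as a contradiction in the text that affects the primary efficacy result. Section 10.2.3 and sections 4.8/7.3 define different populations for the 60-day endpoint, and no passage says which governs. It must be corrected whatever the size of the effect.

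The size is unknown. Under 10% uptake equal across arms, and the assumed risks above, apparent efficacy ranges from 68.9/79.1/87.4% to 75/83/90% against 70/80/88% planned, and the group 3 minus group 1 difference from 18.6 to 15.0 points against 18.0. Uptake, relative risk and the share of failures removed are all assumptions. Unequal uptake, the route to a spurious arm difference, is outside this illustration.

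**What to change.** - In 4.8, 7.3 and 10.2.3, state that the primary efficacy analysis keeps antibiotic users in the intent-to-treat population.
- Continue these subjects' already scheduled stool collection and toxin testing through the day 60 visit.
- Count any recurrence that meets the section 6 definition within 60 days as a failure, whether or not another antibiotic was taken.
- Add to 10.2 one rule, applied to all intent-to-treat subjects, for a missing day 60 outcome. Section 10.2 has none at present.
- Make exclusion of non-C. difficile antibiotic users a sensitivity analysis.
- Align the scope of 4.8 (any systemic antibiotic) with 7.3 (non-C. difficile antibiotics), as a wording change only.

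The cost is protocol wording and a few more scheduled samples to collect and test from a minority of subjects. The efficacy figures may come out less favourable.

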4.9 Termination of Study

Although the Principal Investigator has every intention of completing the study, he may terminate the study at any time for clinical, safety or administrative reasons.

5. INVESTIGATIONAL PRODUCT PRIM-DJ2727 (MICROBIOTA SUSPENSION)

5.1 Manufacture and Storage

PRIM-DJ2727 is manufactured by using current Good Laboratory Practices in The University of Texas Health Science Center at Houston School of Public Health's Enteric Pathogen Diagnostic Laboratory (EPDL) which is a CLIA and CAP-certified laboratory. The FMT product for each treatment group contains bacteria from $\geq 100g$ filtered stool

from healthy donors. Product will be lyophilized at the University of Texas School of Public Health [REDACTED], and compounded and packaged into capsule formulation at the [REDACTED]. Because of individual diet variation in the donors and the FMT product being lyophilized, the number of FMT capsules produced for each dose varies depending on the density of end product. Therefore, placebo capsules will be added to doses to maintain consistent number of capsules per treatment. Placebo capsules will be identical to the investigational product but will not contain intestinal bacteria. After packaging into capsules, the PRIM-DJ2727 will be stored in a sterilized refrigerator at 4°C at the EPDL for up to 6 months in a test tube rack clearly labelled with the lot number and expiration date.

5.2 Dose of FMT Product

Subjects will receive varying doses of PRIM-DJ2727 on two consecutive days of FMT. The clinical team will receive medications for each subject in labeled (see CMC protocol for label details) standard opaque pharmacy-type plastic containers for Day 1 or Day 2. Because of adding placebo capsules to maintain consistent number of capsules per treatment, the clinical trial personnel and subjects will be blinded as to the drug dose allocation.

Subjects in group 1 will receive healthy microbiota collected from 50g stool for 2 consecutive days with bowel prep and Imodium. Subjects in group 2 will receive healthy microbiota collected from 100g stool on the 1st day of treatment and from 50g stool on the 2nd day of the treatment with bowel prep and Imodium. Subjects in group 3 will receive healthy microbiota collected from 100g stool for two consecutive days with bowel prep and Imodium. Subjects in unblinded group 4 will receive healthy microbiota collected from 100g stool for two consecutive days without bowel prep and Imodium.

5.3 Method of Assigning Subjects to Study and Treatment

The four groups will be assigned randomly on 1:1:1:1 ratio by computer table randomization method at the University of Texas School of Public Health. After enrollment of subject in the study, the study coordinator will send an email to the authorized person for randomization at the University of Texas School of Public Health including the schedule (date and time) of study procedure. The study coordinator will receive an email from the authorized person providing the subject identification number and confirmation of date and time for study drug delivery. For subjects randomized to unblinded treatment group 4, it will be noted in the email not to use bowel prep and Imodium.

